- [4] K-MMSE: The results of a test performed at the study site within 2 weeks prior to the screening visit may be used if available.
- [5] Brain CT: This will be performed only on subjects without brain CT imaging within 12 months prior to the screening visit.
- [6] Collecting human-derived samples: Human-derived samples (DNA, plasma, serum, and cerebrospinal fluid) will be collected for exploratory evaluations, and they will be transferred to the central lab for analysis and storage. However, in the case of cerebrospinal fluid, it will be collected only from subjects who have separately consented to collection of samples. For Visit 1 (screening), separate visits for collecting human-derived samples can be set up and implemented within the screening period.
- [7] Investigational product administration: Subjects will be observed for approximately 20 minutes after the administration of the investigational product from Visit 2 to Visit 15.
- [8] Adverse events assessment: Adverse events that occurred after the first administration of the investigational product will be identified, and prior to the first administration, it will be collected as medical history.

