10.2. Evaluation Items by Visit

10.2.1. Visit 1 (Screening, From -4 Weeks)

After the consent procedures of the subject and/or the subject's representative are completed and the written informed consent form is obtained, the following evaluations will be performed after the screening number is assigned. However, a written consent may be obtained prior to Visit 1 (screening), and the tests that could not be performed at Visit 1 (screening), they may be performed at a revisit within the screening period.

- The demographic information of the subject, medical/surgical history, and prior/concomitant drug administration history will be investigated.
- A physical examination will be performed.
- Vital signs will be measured.
- Weight and height will be measured.
- Electrocardiography will be performed.
(However, the results of a test performed within 3 months may be used if available, and retesting may be performed only once at the discretion of the investigator.)
- Laboratory tests will be performed.
(However, the results of tests performed within 4 weeks may be used if available, and retesting may be performed only once at the discretion of the investigator. The serum FSH tests shall be performed to confirm menopause in women aged ≥ 41 years to < 55 years who have experienced amenorrhea for more than 1 year.)
- Urine hCG pregnancy tests will be performed only for women of childbearing potential, excluding subjects confirmed to have undergone surgical sterilization and as being menopausal.
(However, the subjects who performed the serum FSH test to confirm menopause when participating in the clinical study will also perform urine hCG pregnancy test.)
- The inclusion/exclusion criteria will be checked.
- The K-MMSE test will be performed.
(However, the results of a test performed at the study site within 2 weeks prior to the screening visit may be used if available.)
- The PSP-rating scale test will be performed.
- A brain CT will be performed only on subjects without brain CT imaging within 12 months prior to the screening visit.
- Human-derived samples (DNA, plasma, serum, cerebrospinal fluid) will be collected for exploratory evaluations. However, in the case of cerebrospinal fluid, it will be collected only from subjects who have separately consented to collection of samples. Separate visits for collecting human-derived samples can be set up and implemented within the screening period.
- The date of the next visit will be designated.

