10.3.12. PSP-rating scale

The PSP-rating scale evaluation will be performed at Visit 1 (screening), Visit 10, and Visit 16, and the baseline of the PSP-rating scale shall be Visit 1 (screening). At the visits requiring an evaluation of the PSP-rating scale, the subject shall make the visit in a 12-hour off-medication state for the oral drugs specified in advance. This is corresponds to a neurological examination that is directly evaluated by a neurologist who has received or is receiving a subspecialty training on dyskinesia, and the scores are summed according to a set form.^{14, 33)}

See [\[Appendix 5\]. PSP-rating scale](#) for details.

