10.3.17. Collecting Human-Derived Samples

Human-derived samples (DNA, plasma, serum, and cerebrospinal fluid) will be collected for exploratory evaluations, and they will be transferred to the central lab for analysis and storage.

Blood collection for DNA, plasma, and serum is performed at Visit 1, Visit 10, and Visit 16, in the case of cerebrospinal fluid, it will be collected only from subjects who have separately consented to collection of samples at Visit 1 and Visit 16. For Visit 1 (screening), separate visits for collecting human-derived samples can be set up and implemented within the screening period.

Samples collected for exploratory evaluations will be stored for 10 years from the termination date of the clinical study and then disposed of according to the regulations of the relevant study site.

The collected samples may be used for similar or comprehensive studies only if the subjects agree to provide them for secondary use in the Human-Derived Samples Consent form, and the samples collected will also be stored for 10 years from the termination date of the clinical study and then disposed of according to the regulations of the relevant study site.

Plasma protein and inflammatory response markers in blood and cerebrospinal fluid will be tested at the central lab, and the test items are as shown below. The baseline of the test results using human-derived samples shall be Visit 1 (screening).

- Total tau (t-Tau), phosphorylated tau (p-Tau), and neurofilament-light chain (NfL) in blood and cerebrospinal fluid
- Inflammatory cytokine markers (IL-6, IL-8, IL-2, IFN- γ , TNF- α , etc.) in blood and cerebrospinal fluid

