10.5. Definition and Reporting of Adverse Events

10.5.1. Definition of Adverse Events

(1) Adverse event (AE)

This refers to any harmful and unintended signs (including abnormal laboratory test results, etc.), symptoms, or diseases that occur in a subject who has been administered an investigational product, and it does not necessarily must have a causal relationship to the investigational product.

(2) Adverse drug reaction (ADR)

This refers to any harmful and unintended reactions that occur at any dose of an investigational product and of which the causal relationship to the investigational product cannot be denied.

(3) Unexpected adverse drug reaction

This refers to a difference in the pattern of an adverse drug reaction or the extent of harm in light of the available information on the drug such as the investigator's brochure or the product insert of the drug.

(4) Serious adverse event/adverse drug reaction (serious AE/ADR)

This refers to an adverse event or adverse drug reaction that occurs at any dose of an investigational product that corresponds to any one of the following:

- ① Occurrence of death or life-threatening risks
- ② Requires hospitalization or prolongation of hospitalization
- ③ Results in permanent or significant disability or functional decline
- ④ Occurrence of malformations or abnormalities in a fetus
- ⑤ Other than cases ① through ④, occurrence of drug dependence or abuse, or cases in which medically significant situations occur, such as hematopathies

However, in this clinical study, a visit made for the following reasons will not be considered as a serious adverse event.

- Hospitalization planned prior to the clinical study
- Hospitalization for medical examination, cosmetic reasons, and recuperation
- Cases in which the time of visiting the emergency room has not exceeded 24 hours. However, it may be considered a serious adverse event based on the investigator's judgment even if it does not exceed 24 hours.

If a situation occurs that is considered to have a significant impact on the patient's well-being and health status, even if not listed above, it shall be determined whether to consider it as a serious adverse event according to the medical judgment of the doctor in charge and relevant specialists, and appropriate measures shall be taken accordingly.

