10.5.2. Reporting of Adverse Events

- Adverse events will be collected during the clinical study from the time point after investigational product administration and up to the final visit. All medical events that occur prior to investigational product administration will be recorded as medical history.
- Adverse events shall be reported by including the name of the adverse event, duration (start date and disappearance date), severity, causal relationship to the investigational product, actions taken for the investigational product, outcome, corrective treatment for the adverse event, and whether the event is a serious adverse event.
- When recording an adverse event, the investigator shall use a comprehensive diagnosis or symptom using standard medical terminology rather than recording each symptom or sign.
- Adverse events that occur during the clinical study shall be followed up until they disappear, show stable outcomes, or the subject is lost to follow-up.
- Adverse events that occur after the end of the clinical study shall be reported only if they are serious and related to the investigational product.

1) Severity Assessment

The investigator will assess the severity of adverse events and serious adverse events by referring to the criteria described below.

Mild	The event causes minimal discomfort without interfering with the subject's normal daily life (function), and it can be easily tolerated by the subject.
Moderate	The event causes discomfort that significantly interferes with the subject's normal daily life (function).

Severe The event makes the subject's normal daily life (function) impossible.

Activities of daily living are defined below.

: All activities that occur in daily life to take care of one's own body (e.g., bathing, dressing and undressing, eating, taking medications, hygiene, and personal care)

An adverse event or serious adverse event can both be evaluated as severe according to the definition above, and one should not be confused for the other since a severe adverse event does not necessarily correspond to a serious adverse event.

2) Causality Assessment

The investigator will assess the causal relationship between an adverse event and the investigational product by referring to the criteria described below. If it is assessed as unlikely, it can be determined as "no causal relationship" (non-ADR). If it is assessed as other items, it will be determined that there is a causal relationship (ADR).

- ① Certain

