10.5.3. Reporting of Serious Adverse Events

All serious adverse events that occur from the time point after investigational product administration and up to the final visit shall be reported to the sponsor via telephone, fax, e-mail, etc., within 24 hours of the investigator's recognition, regardless of their relationship to the investigational product, and they must be reported to the IRB of the affiliated study site within the timeline specified by the IRB.

Adverse events that occur after the end of the clinical study shall be reported only if they are serious and related to the investigational product.

When reporting serious adverse events to the sponsor, the investigator shall use the subject identification code instead of the subject's personal information such as the name, resident registration number, and address in order to protect the confidentiality of the subject's identity. Even if copies of some medical records are requested as needed, the personal information, except the identification code, will be redacted.

If the investigator becomes aware of any additional information on reported serious adverse events, a follow-up report shall be made. The investigator shall conduct follow-ups and submit reports to the sponsor and the IRB until the corresponding serious adverse event disappears, shows a stable outcome, or the subject is lost to follow-up.

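### Adverse event collection and 24-hour SAE reporting begin only after the first dose, so harm from the Visit 1 CSF collection and 12-hour off-medication assessment is recorded only as medical history

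*Combined protocol and SAP*

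**What the plan says.** **Start of collection.** Protocol 10.5.2 says: "Adverse events will be collected during the clinical study from the time point after investigational product administration and up to the final visit". For anything earlier it says: "All medical events that occur prior to investigational product administration will be recorded as medical history". Protocol 10.3.19 and footnote 8 of the schedule repeat the rule. In SAP 3.4 the footnote reads: "prior to the first administration, it will be collected as medical history".

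**SAE reporting.** Protocol 10.5.3 opens the 24-hour duty at the same point: "All serious adverse events that occur from the time point after investigational product administration and up to the final visit shall be reported".

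**Definition.** Under protocol 10.5.1 an AE is an event "that occur in a subject who has been administered an investigational product". A pre-dose event is therefore not formally an AE, nor an SAE.

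**What happens before the first dose.** At Visit 1, protocol 10.2.1 says: "Human-derived samples (DNA, plasma, serum, cerebrospinal fluid) will be collected for exploratory evaluations". CSF is optional; under 10.3.17, "it will be collected only from subjects who have separately consented to collection of samples at Visit 1 and Visit 16". Visit 1 also includes the baseline PSP-rating scale, and for every visit with that scale 10.3.12 requires that "the subject shall make the visit in a 12-hour off-medication state for the oral drugs specified in advance". The first dose is given at Visit 2, which 10.2.2 places within 4 weeks of Visit 1.

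**The concern.** Starting AE collection at the first dose is a defensible choice for tables meant to describe the drug. It fits less well when the protocol itself asks for an invasive, non-therapeutic sample and a period off usual medication before that dose. A serious complication of the Visit 1 CSF collection, or an injury during the off-medication period, would be entered as medical history by a site following the text exactly. It would have no seriousness, severity or causality assessment, and no timed report to the sponsor.

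What is at stake is subject protection, not the efficacy analysis. If such events cluster, the sponsor and any data monitoring committee convened under 11.2.4.1 have no assured, timely route by which to learn of them while screening continues.

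**Working it through.** No power, alpha or event figure bears on this point, and the plan states no figure to reproduce. The check sets the reporting window against the procedure schedule, then looks for other routes by which an event could be reported.

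**1. The window.** It opens after the first dose at Visit 2 (10.3.19, 10.5.1, 10.5.2, 10.5.3, footnote 8). The longest uncovered period after Visit 1 is 4 weeks × 7 days = 28 days. This is a maximum: Visit 2 may come sooner, and 10.2.1 lets samples be taken at a separate visit later in screening.

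**2. Procedures against the window.**

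| Procedure | Scheduled visits | Before first dose | Share outside |
|---|---|---|---|
| CSF collection (10.3.17) | 1, 16 | 1 | 1 of 2 |
| PSP-rating scale, 12 hours off medication (10.3.12) | 1, 10, 16 | 1 | 1 of 3 |

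**3. What an event record holds.** An AE report under 10.5.2 includes severity, causality, seriousness, outcome, action taken and treatment. Medical history under 10.3.3 records time of occurrence and whether the condition persists at screening; no seriousness, severity or causality is asked for. SAP 8.5.1 then classifies each entry only by whether it is ongoing.

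**4. Who appears in the outputs.** SAP 8.5.2 summarises and lists medical history for the Randomized Set. A subject harmed at Visit 1 who then fails screening is not in that set. Disposition (SAP 8.1) lists screen failures and summarises the reasons, but that is not a safety record. Visit 2 rechecks medical history (10.2.2), which does not help for a subject who never reaches Visit 2.

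**5. Procedure causality.** The causality scale in 10.5.2 relates events to the investigational product only. No field records a relationship to a study procedure.

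**6. Other routes.** Protocol 11.2.4.2 has the principal investigator report unexpected problems to the sponsor and IRB. Protocol 13.5.1 has life-threatening issues and deaths reported to the Ministry and/or IRB. Neither depends on dosing. Neither sets a 24-hour limit or mentions screening procedures. The clause in 13.5.1 does not name hospitalisation or lasting disability that is not life-threatening, both of which are SAE criteria in 10.5.1. A known complication of CSF sampling might also not be judged unexpected.

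**7. Number exposed.** First CSF collections outside the window = subjects screened × proportion consenting to CSF. The documents give neither term: 75 is the randomization target, and no screen-failure or CSF consent rate is stated. The number with an actual 12-hour withdrawal is also unknown, since it depends on who takes the specified oral drugs.

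**The case against.** The strongest reply is that the rule is a consistent design choice. Every section uses the same starting point, the stated safety aim concerns GV1001 rather than sampling procedures, and the treatment-emergent analysis is unaffected. Pre-dose events do leave a record: Visit 2 repeats the history check, physical examination, vital signs and laboratory tests, and medical history is MedDRA-coded and listed for randomized subjects. The separate sample-consent form, which might hold CSF-specific provisions, is not available for review. All of this stands, and it limits the point to grading, timed reporting and screen failures.

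Some stronger readings are tempting but not supported:

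- *Such harm is never reported, and the sponsor and IRB could not see it.* The clauses in 11.2.4.2 and 13.5.1 are not tied to dosing and could bring some events forward. What is missing is an assured, timed route.
- *Procedure-related events are lost throughout the trial.* After the first dose, 10.5.3 requires SAE reports regardless of relationship to the product. The CSF collection at Visit 16 and the off-medication assessments at Visits 10 and 16 lie inside the window, and the Visit 17 telephone contact asks about AEs after Visit 16. Those events are captured, though without a procedure-causality field.
- *All 75 randomized subjects undergo an unmonitored CSF collection.* Collection is optional and needs separate consent. An assumed consent rate applied to 75 would only restate the assumption.
- *A known complication rate applies.* The documents give no rate of complications or falls, and they do not name the technique used to obtain CSF.

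**Conclusion.** The concern holds in a limited form. For up to 28 days between Visit 1 and the first dose, harm from study-imposed procedures falls outside AE grading and 24-hour SAE reporting. This affects one of two CSF collections and one of three off-medication assessments. Harmed screen failures are also missing from the medical-history outputs. The general reporting clauses reduce the gap but do not close it.

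The conclusion rests on the protocol and SAP text as available, and assumes that no other study document, such as the sample-consent form, starts SAE reporting earlier. The number of subjects affected is unknown. No efficacy result or treatment-emergent table depends on this point. It is an inexpensive improvement in subject safety that should be made, not a flaw in the trial's inference.

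**What to change.** Amend protocol 10.3.19, 10.5.1, 10.5.2 and 10.5.3, and schedule footnote 8 wherever it appears in the protocol and SAP, so that from signed consent to first dose:

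- all SAEs are reported to the sponsor within 24 hours;
- any AE judged related to a study procedure (CSF collection, blood draw or the off-medication period) is recorded as an AE;
- both rules apply to screen failures;
- other pre-dose events stay as medical history.

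The AE definition in SAP 10.2.1 repeats that in 10.5.1 and should be changed with it. Add a field to the AE form for relationship to a study procedure, and show pre-dose events in a separate listing that includes screen failures.

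SAP 10.2.1 defines treatment-emergent events relative to exposure and protocol 11.2.10.1 bases the AE analysis on them, so those tables do not change. SAP 10.2.2 speaks of AEs in general; one sentence confining its tables to treatment-emergent events would keep the new pre-dose records out of them.

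The cost is a short protocol amendment, a small eCRF change, one extra listing and a few more SAE forms during screening. No visit or test is added.

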10.5.3. Reporting of Serious Adverse Events

All serious adverse events that occur from the time point after investigational product administration and up to the final visit shall be reported to the sponsor via telephone, fax, e-mail, etc., within 24 hours of the investigator's recognition, regardless of their relationship to the investigational product, and they must be reported to the IRB of the affiliated study site within the timeline specified by the IRB.

Adverse events that occur after the end of the clinical study shall be reported only if they are serious and related to the investigational product.

When reporting serious adverse events to the sponsor, the investigator shall use the subject identification code instead of the subject's personal information such as the name, resident registration number, and address in order to protect the confidentiality of the subject's identity. Even if copies of some medical records are requested as needed, the personal information, except the identification code, will be redacted.

If the investigator becomes aware of any additional information on reported serious adverse events, a follow-up report shall be made. The investigator shall conduct follow-ups and submit reports to the sponsor and the IRB until the corresponding serious adverse event disappears, shows a stable outcome, or the subject is lost to follow-up.

10.5.4. Reporting Procedures for Suspected Unexpected Serious Adverse Reactions (SUSARs)

In the case that suspected unexpected serious adverse reactions (SUSARs) occur during the study period, the sponsor shall report them to the investigator, the Minister of Food and Drug Safety, and the IRB within the period specified in each of the following paragraphs. For details, see “Regulations on the Safety of Drugs, etc.” Appendix 4 Korean Good Clinical Practice for Drugs and the guide for civil petitioners, “Considerations for Safety Evaluation and Reporting of the Sponsor of Clinical Trial for Drugs.”

- ① For unexpected adverse drug reactions that result in death or are life-threatening, they shall be reported as soon as possible via telephone, fax, and documents within 7 days from the date the sponsor was initially reported of the relevant fact or became aware of it. If not all of the information was reported according to the adverse drug reaction report, a detailed report shall be additionally submitted within 15 days from the date the sponsor was initially reported of the relevant adverse drug reaction or became aware of it.
- ② All other SUSARs shall be reported within 15 days from the date the sponsor was reported of the relevant fact or became aware of it.

In the case that suspected unexpected serious adverse reactions (SUSARs) occur during the clinical study, the principal investigator and study staff members shall make every effort for the safety of the subjects, and take prompt and appropriate actions to minimize the adverse events. If additional information on the reported adverse drug reaction is available, the sponsor shall report it until the corresponding adverse drug reaction is ended (refers to the disappearance of the corresponding adverse drug reaction or becoming impossible to follow up).

If the clinical study is conducted at multiple study sites, the sponsor shall promptly notify the study sites through the principal investigators.

